
• The investigator will make an assessment of intensity for each ADE/ SADE/ device deficiency reported during the study and assign it to one of the following categories:• Mild: An event that is easily tolerated by the participant, causing minimal discomfort and not interfering with everyday activities.• Moderate: An event that causes sufficient discomfort and interferes with normal everyday activities.• Severe: An event that prevents normal everyday activities. An ADE that is assessed as severe should not be confused with an SADE. Severe is a category used for rating the intensity of an event; both ADEs and SADEs can be assessed as severe.• An event is defined as ‘serious’ when it meets at least 1 of the predefined outcomes as described in the definition of an SADE, not when it is rated as severe.
Assessment of Causality

• The investigator is obligated to assess the relationship between study intervention and each occurrence of each ADE/SADE/device deficiency• A “reasonable possibility” of a relationship conveys that there are facts, evidence, and/or arguments to suggest a causal relationship, rather than a relationship cannot be ruled out.• The investigator will use clinical judgment to determine the relationship.• Alternative causes, such as underlying disease(s), concomitant therapy, and other risk factors, as well as the temporal relationship of the event to study intervention administration will be considered and investigated.• The investigator will also consult the Investigator’s Brochure (IB), in his/her assessment.• For each ADE/SADE/device deficiency, the investigator must document in the medical notes that he/she has reviewed the ADE/SADE/device deficiency and has provided an assessment of causality.• There may be situations in which an SADE has occurred and the investigator has minimal information to include in the initial report to GSK. However, it is very important that the investigator always make an assessment of causality for every event before the initial transmission of the SADE data to GSK.• The investigator may change his/her opinion of causality in light of follow-up information and send an SADE follow-up report with the updated causality assessment.

- The causality assessment is one of the criteria used when determining regulatory reporting requirements.

Follow-up of SADE/device deficiency

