4.4.2. Serious Adverse Events and Other Safety Reporting

Reporting of safety analyses includes the analysis of adverse device effects (ADEs), Serious AEs (SAEs), Serious ADEs (SADEs) and other significant ADEs will be based on GSK Core Data Standards.

Adverse events (AEs) will not be reported for this study. Instead, ADEs will be captured using the standard CDISC AE eCRF in conjunction with the Medical Device Deficiency eCRF. An ADE is defined as an AE for which the investigator classifies the relationship to Medical Device Deficiency for a non-serious adverse event as “Yes”, where the start date of the AE occurs on the same date as the device deficiency.

Adverse events to identify ADEs will be coded using the standard Medical Dictionary for Regulatory Affairs (MedDRA dictionary), with the maximum severity of each AE determined by

the investigator (as mild, moderate or severe). A Standardised MedDRA Query (SMQ) will be used to identify all COVID-19 AEs.

An overview summary of ADEs, including counts and percentages of participants with any ADE and ADEs leading to discontinuation of the study inhaler (and therefore withdrawal from the study) will be produced. The summary tables will be displayed by SOC and PT.

The number and percentage of participants experiencing at least one ADE during the study, in which the medical device is used, will be summarised by each inhaler separately. Additionally, summaries of the number and percentage of participants with any ADEs by maximum severity will be produced. If an adverse event severity is missing, the severity is to be populated as “UNKNOWN”.

The frequency and percentage of ADEs will be summarized and displayed in two ways:
1) in descending order by SOC and PT and 2) in descending order by PT only.

Common ADEs, defined as $\geq 3\%$ (prior to rounding) in any inhaler group, will be reported. The summary table will be displayed by PT only.

A worst-case scenario approach will be taken to handle missing relatedness data, i.e. the summary table will include events with the relationship to study inhaler as “Yes” or missing. The summary table will be displayed by SOC and PT.

The number and percentage of participants experiencing at least one SAE during the study will be summarised.

The number and percentage of participants experiencing at least one SADE during the study, in which the medical device is used, will be summarised by each inhaler separately.

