Listings will be presented separately for SAEs and SADEs. All SAEs, SAEs related to study treatment, fatal SAEs, fatal SAEs related to study treatment, all SADEs, fatal SADEs, and fatal SADEs will be produced. In addition, fatal and non-fatal SAEs, and, fatal and non-fatal SADEs will be reported separately.

A study treatment-related SAE is defined as an SAE for which the investigator classifies the relationship to study treatment (i.e. placebo) as “Yes”. A worst-case scenario approach will be taken to handle missing data, i.e. the summary table will include events with the relationship to study treatment as “Yes” or missing. The summary tables will be displayed by SOC and PT.

An SADE is defined as an SAE for which the investigator classifies the relationship to Medical Device Deficiency for a serious adverse event as “Yes”. A worst-case scenario approach will be taken to handle missing data, i.e. the summary table will include events with the relationship to study treatment as “Yes” or missing. The summary tables will be displayed by SOC and PT.

The incidence of AEs and SAEs (Fatal and Non-Fatal) of COVID-19, COVID-19 AEs leading to study inhaler discontinuation, COVID-19 AEs leading to study withdrawal, and COVID-19 AEs by maximum severity, will be obtained from the standard AE and SAE summaries.

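### The SAP defines a SADE by relationship to the device but keys its worst-case missing-data rule to relationship to study treatment (placebo), so the by-inhaler SADE table has no consistent inclusion rule

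*SAP*

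**What the plan says.** SAP 4.4.2 handles the two kinds of serious event in adjacent paragraphs.

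- **Treatment-related SAE.** This is an SAE for which "the investigator classifies the relationship to study treatment (i.e. placebo) as" Yes. For missing data, "the summary table will include events with the relationship to study treatment as" Yes or missing. Definition and rule use the same field.
- **SADE.** "An SADE is defined as an SAE for which the investigator classifies the relationship to Medical Device Deficiency for a serious adverse event" as Yes. The missing-data sentence that follows is identical to the one above, still naming study treatment. Definition and rule use different fields.

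Earlier in the same section, the ADE definition also rests on relationship to Medical Device Deficiency, but its worst-case rule uses a third term: "the summary table will include events with the relationship to study inhaler as" Yes or missing.

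The output affected is a SADE result given separately for the two inhalers. The SAP's sentence for it begins: "The number and percentage of participants experiencing at least one SADE during the study, in which the medical device is used, will be summarised by". SAEs are also summarised as a whole, and "Listings will be presented separately for SAEs and SADEs". The SAP version history records that version 2 added the SAE and SADE summary tables, where only listings had been specified before.

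Protocol Appendix 7 (10.7.4, causality) words the judgement differently: "The investigator is obligated to assess the relationship between study intervention and each occurrence of each ADE/SADE/device deficiency".

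**The concern.** A worst-case rule keeps an event in the table when the judgement that defines the table is unknown. Here the rule looks at another judgement. The SADE table may then lose events whose device causality is unknown, and it may be populated by a field that says nothing about the device. The two fields can plausibly differ: Protocol 2.3.1 names hypersensitivity to lactose in the placebo as a study risk, and an investigator could attribute such a reaction to the powder and not to the inhaler.

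SADE incidence is a stated safety endpoint and is reported separately for the sponsor's inhaler and a competitor's in an open-label study. Which events are charged to which device should not depend on how a programmer resolves two sentences that disagree.

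**Working it through.** No sample size, power or event count enters this point, so the check is an enumeration.

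**Inputs.** D is relationship to Medical Device Deficiency, the field in the SADE definition. T is relationship to study treatment, the field in the SADE missing-data sentence. Each can be Yes, No or Missing, which gives 3 × 3 = 9 combinations. Both come from SAP 4.4.2.

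**Comparator.** A worst-case rule consistent with the definition includes an SAE when D is Yes or Missing, whatever T is. Here Missing means an assessment that was due and not recorded.

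**Readings.** The SAP does not say how the definition and the missing-data sentence combine. Three ways are possible:

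1. The sentence replaces the definition: T is Yes or Missing.
2. Both must hold: D is Yes, and T is Yes or Missing.
3. Either suffices: D is Yes, or T is Yes or Missing.

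| D | T | Device-keyed | Reading 1 | Reading 2 | Reading 3 |
|---|---|---|---|---|---|
| Yes | Yes | in | in | in | in |
| Yes | No | in | **out** | **out** | in |
| Yes | Missing | in | in | in | in |
| No | Yes | out | **in** | out | **in** |
| No | No | out | out | out | out |
| No | Missing | out | **in** | out | **in** |
| Missing | Yes | in | in | **out** | in |
| Missing | No | in | **out** | **out** | **out** |
| Missing | Missing | in | in | **out** | in |
| Included | | 6 | 6 | 2 | 7 |

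Bold marks disagreement with the device-keyed rule.

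- Reading 1: 2 combinations dropped and 2 added. The total of 6 matches the comparator, but 4 combinations differ. The SADE table would have the same inclusion rule as the treatment-related SAE table.
- Reading 2: 4 dropped, none added.
- Reading 3: 1 dropped, 2 added.
- Device Missing with treatment No is excluded under all three.
- Some disagreements involve fully recorded data: device Yes with treatment No (readings 1 and 2), and device No with treatment Yes (readings 1 and 3). The mismatch is not confined to missing values.

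**Size of one event.** If all 114 planned participants use both inhalers (the protocol expects no withdrawals), one misplaced participant changes an inhaler's SADE incidence by 1/114 = 0.9%. This illustrates a single event and is not a forecast.

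**The case against.** **Study treatment may include the inhaler.** SAP 1.2 treats study treatment as complete once both inhalers have been demonstrated, Protocol 6.1 lists the interventions as placebo dry powder inhalers, and Appendix 7 assesses SADE causality against study intervention. On that view the sentence is loose wording for the device. This has some weight, and the eCRF layout is not shown. But the preceding paragraph equates study treatment with placebo, and the SADE definition names a separate device field. If a single field was meant, the SAP needs to say so.

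**A missing-data sentence should not override a definition.** An event with device relationship recorded as No has no missing device datum and fails the definition. This is a fair argument against readings 1 and 3, and so against counting a placebo reaction as a SADE. It does not rescue the rule, because reading 2 drops every SAE with device relationship missing.

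**Missing causality should be rare.** The protocol requires the investigator to "always make an assessment of causality for every event before the initial transmission of the SADE data to GSK". That stands for missing values, but not for the fully recorded combinations in the table.

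**Other conventions may exist.** SAP 1 leaves further data-handling detail to the Output and Programming Specification, which is not available here. It may settle the point, but the SAP as written does not.

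Two stronger inferences are tempting. A reader might conclude that the plan both drops all SAEs with missing device causality and counts placebo-related, not-device SAEs as SADEs. No single reading gives both in full: all missing-device SAEs are dropped only under reading 2, which adds nothing, and under readings 1 and 3 a missing-device SAE is dropped only when treatment is No. A reader might also conclude that a serious event could disappear from the report. It could not: all SAEs are summarised and listed, and Protocol 9.4.3 provides narratives for SAEs and SADEs.

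**Conclusion.** The rule is wrong as written. The SADE definition and its worst-case rule name different causality fields, and none of the three ways of combining them gives the result that a device-keyed worst-case rule would give. The finding common to all three is that an SAE with device relationship missing and treatment relationship No leaves the by-inhaler SADE summary. The other misplacements depend on the reading chosen.

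This rests on taking study treatment as the placebo, as the SAP's own gloss does. The consequence is limited to the placing of events in one safety summary; the primary and secondary efficacy analyses are untouched. The documents give neither an SAE rate nor a missing-causality rate, so the effect cannot be calculated. In a one-day placebo study it is probably an event or two at most. The case for correcting it is that it governs a stated safety endpoint, reported per device, and is easy to put right.

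**What to change.** In the SADE paragraph of SAP 4.4.2, replace the study-treatment field in the missing-data sentence with the device-relationship field that defines a SADE. Include SAEs where that field is Yes, or missing where the assessment was required. State that a blank left because no device deficiency was recorded is not missing. Without that limit, and if the eCRF leaves the field empty when there is no deficiency, the rule could turn every SAE into a SADE. Confine the study-treatment field to treatment-related SAEs.

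For ADEs, use one device-relationship field in both the definition and the missing-data rule, reconciled with Protocol 10.7.1, which defines an ADE by relation to the use of the device. Simply substituting the deficiency field for the study-inhaler wording is not advised, because the existing wording already concerns the device and is closer to the protocol.

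The cost is a few phrases in the SAP before database lock and a check of the eCRF field layout. No additional data are needed.

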4.4.2.1. Impact of COVID-19 Pandemic on Adverse Event Reporting

The number of participants with probable, suspected or confirmed COVID-19 infection will be reported. This display will also summarise the number of participants with a COVID-19 diagnosis test performed and the number of participants with positive, negative, or indeterminate results.

Additionally, a listing of COVID-19 assessments and symptoms for participants with COVID-19 AEs will be generated.

4.4.2.2. Cardiovascular Events and Deaths (All Causes)

Cardiovascular events and deaths (all causes) will be captured on targeted CV event eCRF pages for the following SAEs:

- Arrhythmias
- Congestive heart failure
- Cerebrovascular events/stroke and transient ischemic attack
- Deep venous thrombosis/pulmonary embolism
- Myocardial infarction/unstable angina
- Peripheral arterial thromboembolism
- Pulmonary hypertension
- Revascularization
- Valvulopathy
- Death (all causes)

Separate patient profiles will be provided of participants for one or more of the above listed events.

4.5. Other Analyses

4.5.1. Subgroup analyses

No Subgroup analyses are planned for this study.

4.6. Interim Analyses

No interim analysis of data is planned for this study.

4.7. Changes to Protocol Defined Analyses

Changes from the originally planned statistical analysis specified in the protocol [(Dated: 05-JAN-2021)] are detailed in [Table 3](#):

Table 3 Changes to Protocol Defined Analysis Plan

Protocol Defined Analysis	SAP Defined Analysis	Rationale for Changes

 Performance evaluable analysis set 	
 Modified intention-to-treat (mITT) 	
 The definition of the two analyses in the protocol and SAP are the same. The terminology has been updated in the SAP to “mITT” for the purpose of producing the programming outputs; more accurately aligned with current CDISC standards.

5. SAMPLE SIZE DETERMINATION

A total of 114 participants will be randomly assigned to study intervention such that approximately 114 evaluable participants complete the study.

The sample size for a 2x2 crossover study is based on the formula presented by (Chow, 2008) and (Lui, 2016). To calculate the conditional odds ratio (via McNemar's) the proportion of participants who have discordant pairs (those who had at least one critical error in one inhaler but not the other) was determined based on expert advice. A panel of 5 experts was convened to consider the evidence from previous studies of similar design [(van der Palen J, 2016), (van der Palen J, 2018)] and with consideration given to observational studies in the literature [(Khassawneh BY, 2008), (Melani AS, 2011), (Arora P, 2014), (Chorão P, 2014), (Takaku Y, 2017), (Ocakli B, 2018)]. A consensus view of the likely error rates that would be observed with the ELLIPTA and BREEZHALER devices was subsequently reached.

A consensus was reached that the proportion of participants who make a critical error in the ELLIPTA inhaler and not on the BREEZHALER inhaler would be 6% and the proportion of patients who make a critical error in the BREEZHALER inhaler and not on the ELLIPTA inhaler would be 20%.

Based on the discordant proportions, an odds ratio of 0.3 was calculated and a standard deviation on the log odds ratio scale of 2.785 was calculated based on GSK study 200301 (van der Palen J, 2016). Based on these estimates and a two-sided Type I error rate of 5%, a total of 114 participants are required to provide 90% power. No withdrawals are expected based on previous similarly designed studies. No correlation between periods is assumed and no carry over effect is assumed based on previous evidence (van der Palen J, 2013). Moreover, both inhalers will contain placebo and participants may have up to a 30-minute break after demonstrating the first inhaler.

6. SUPPORTING DOCUMENTATION

6.1. Appendix 1 Abbreviations and Trademarks

6.1.1. List of Abbreviations

Abbreviation	Description
ADE	Adverse device effect
AE	Adverse Event
CDISC	Clinical Data Interchange Standards Consortium
CI	Confidence Interval
COVID-19	Coronavirus Disease-2019
CSR	Clinical Study Report
eCRF	Electronic Case Record Form
FAS	Full analysis set
GSK	GlaxoSmithKline
mITT	Modified Intention-to-Treat
OPS	Output and Programming Specification
SAP	Statistical Analysis Plan
SAE	Serious adverse event
SADE	Serious adverse device effect
VAS	Visual Analogue Scale

6.1.2. Trademarks

Trademarks of the GlaxoSmithKline Group of Companies	Trademarks not owned by the GlaxoSmithKline Group of Companies
ELLIPTA	SAS BREEZHALER WinNolin

